7. TREATMENT COMPARISONS

7.1. Data Display Treatment and Other Sub-Group Descriptors

Planned groups to be displayed on the summary tables are based on the cohort corresponding to initial dose as determined by subject weight/weight band at study baseline:

Cohort	Dose	Weight Band (at baseline)
1	150 mg capsule	≥40 kg
2	108 mg granules	32 to <40 kg
3	96 mg granules	24 to <32 kg
4	78 mg granules	12 to <24 kg
All Cohorts	All Doses	12 to ≥40 kg

Unless otherwise noted, tables will be arranged by cohort, and listings will be sorted by cohort, subject number, and date. Subjects will be analyzed by their original assigned cohort. Subjects who have their dose changed (decreased or increased) may be footnoted in Tables and Figures (eg, 1 subject in Cohort 1 had a dose decrease to xxx mg in Part x or Week xx). In addition, a listing of subjects with dose increases or decreases will be generated.

8. GENERAL CONSIDERATIONS FOR DATA ANALYSES

All statistical analyses will be conducted with the SAS® software package version 9.4 or higher. All analyses will be subject to formal verification in accordance with PharPoint's SOPs. Specifically, results will be verified utilizing independent programming prior to issuance of the draft statistical reports. All documents will be verified by the lead statistician to ensure accuracy and consistency of analyses.

All data collected during the study will be included in data listings.

The following considerations do not apply to the population PK analyses. Considerations for those analyses will be presented in the population PK analysis plan.

8.1. Multicenter Studies

This study will enroll subjects across multiple study centers in North America, Israel, and Europe.

8.2. Other Strata and Covariates

No stratification or adjustment for covariates is planned.

8.3. Examination of Subgroups

No subgroup analyses are planned.

8.4. Multiple Comparisons and Multiplicity

No adjustment for multiple comparisons is planned.

8.5. Data Handling Conventions

8.5.1. Premature Withdrawal and Missing Data

For subjects who prematurely discontinue the study, all available data will be included for the key safety and effectiveness analyses. No imputation for missing data will occur.

Dropouts will not be replaced.

8.5.2. Missing Start and Stop Dates for Prior and Concomitant Medication

For analysis of medications, a complete date should be established to identify whether a medication was taken during the study treatment period or not. The following algorithm will be applied to handle partially reported start and stop dates for medications:

- Missing start day, but month and year present:

If study medication had been taken in the same month and year as the occurrence of the medication, then the start day of the event/medication will be assigned to the day of first dose of study medication.

Otherwise, the start day will be set to the first day of the month.

- Missing start day and month, but year present:

If study medication had been taken in the same year as the occurrence of the medication, then the start date of the medication will be assigned to the date of first dose of study medication.

Otherwise, the start day and month will be set to 01 January.

- Missing end day, but month and year present:

The day will be set to the last day of the month.

- Missing end day and month, but year present:

The end day and month will be set to the date of study termination.

However, if study termination year is greater than the year of the event/medication, then the day and month will be set to 31 December.

- Completely missing start date:

For HAE medications collected on subject diaries, the date will be set to the corresponding HAE attack date. For all other concomitant medications, a completely missing start date will be set to the treatment start date (if prior to the medication end date) or otherwise will be set to the medication end date.

In subject data listings, start and stop date of medication will be displayed as reported on the eCRF.

8.5.3. Missing Start and Stop Dates for Adverse Events

The same conventions for addressing incomplete dates for prior and concomitant medications will also be used for AEs.

8.5.4. Missing Assessment Time for Laboratory, Vital Sign, PK, or ECG Measurement

For assessments with missing times, the timepoint, if available, will be utilized to determine if the assessment occurs pre- or post-dose. For Day 1 assessments without a planned post-dose evaluation, any assessment with no associated time will be considered as obtained prior to the initiation of berotralstat (ie, pre-dose).

8.5.5. Missing AE Start Time or End Time

For AEs with missing start or end times the duration will be calculated using only dates. As noted above, AEs with missing start times that occur on Day 1 will be considered as treatment emergent.

8.5.6. Missing Time of First and Last Dose

In case of missing time for first dose, it will be assumed that baseline pre-dose measures that were to be taken prior to first dose according to the protocol were in fact taken prior to dosing.

In case the time of the last dose is not reported on the diary, time of dose will be assigned as the median dosing time from all prior doses for the subject, as subjects are to dose once per day at approximately the same time each day.

8.5.7. Incomplete Date and Time for a Subject-Reported Attack

For HAE attacks reported with a missing start/stop date and or time, the following algorithm will be applied:

- Missing start time but start date present:

The start time will be set to 12:00PM.

- Missing start date and time:

The start date will be set to the diary date for which the question was answered “Yes”.
The start time will be set to 12:00PM.

- Missing stop time, but stop date present:

The stop time will be set to 11:59PM.

- Missing stop date and time:

The stop date will be set to the attack start date, and the stop time will be set to 11:59PM.

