4. INTRODUCTION

4.1. Background

Hereditary angioedema (HAE) with C1-esterase inhibitor (C1-INH) deficiency is an autosomal dominant disorder characterized by recurrent episodes of swelling of the skin, pharynx, larynx, gastrointestinal (GI) tract, genitals, and extremities (Longhurst and Cicardi 2012). The frequency of attacks varies between subjects, from rarely in some patients to every few days in others. Angioedema attacks may or may not be precipitated by a stimulus (such as stress, trauma, or estrogen) and are typically rapid in onset, with symptoms subsiding gradually over the following 3 to 5 days (Zuraw and Christiansen 2011). Oropharyngeal swelling can be life-threatening (Bork, Hardt et al. 2012), while attacks in other sites, including limbs, genitalia, face, and intestines, can be painful, disabling, and disfiguring, and have a significant impact on functionality and quality of life (QoL) (Lumry, Castaldo et al. 2010). Although mortality risk from asphyxiation is much higher in undiagnosed patients with HAE, deaths still occur in diagnosed patients with access to care at centers of excellence (Bork, Hardt et al. 2012).

Extensive evidence from animal models and clinical studies supports the role of bradykinin (BK) as the principal mediator of the signs and symptoms that characterize attacks of HAE (Han, MacFarlane et al. 2002, Kaplan 2010, Zuraw and Christiansen 2011). Plasma kallikrein is a serine protease integral to the contact activation pathway (Saxena, Thompson et al. 2011). Kallikrein circulates in plasma as a zymogen, prekallikrein (PKK), bound to one of its main substrates, high-molecular-weight kininogen (HK). During contact activation, PKK is cleaved by activated factor XII, forming the active protease kallikrein. Kallikrein in turn cleaves HK, producing BK (Kaplan and Ghebrehiwet 2010). The activation of the bradykinin B2 receptor by BK ultimately results in vasodilatation, increased vascular permeability, and smooth muscle contraction, all of which lead to the tissue swelling that characterizes HAE (Kaplan 2010).

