10.11. HAE Attack Diary

The sponsor will supply paper diaries to sites to be distributed to the P/C for recording the subject's HAE attacks. The P/C will fill out the HAE attack diary whenever an attack (or suspected attack) occurs. If the subject reports an attack or if the P/C suspects that an attack has occurred, additional details should be entered into the diary including start and stop time of the attack, attack symptoms, anatomical location of swelling (if applicable), severity, treatment(s) administered and times of administration, and whether additional medical care was sought for the attack. Subjects will complete the diaries from enrollment through the end of Part 2 (ie, Week 48).

The P/C will be instructed to bring the subject's diary with them to each study visit. Diaries will be collected at each visit through Week 48, and new diaries will be dispensed at each visit prior to Week 48.

Subjects who withdraw from the study should continue to record the occurrence of HAE attacks in their diary until they return to the site for the appropriate EOS visit.

Once a subject completes or discontinues the study, the site must collect all diaries from the P/C. Study staff are not permitted to make any entries into the diary.

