6.7.7.2. Adjusted Attack

Subject-reported attacks reported must meet the following criteria (applied in order) for inclusion in effectiveness analyses:

- Attack must include at least 1 symptom of swelling;
- Subject response to diary question, “In retrospect, could there be an alternative explanation for your symptoms other than an HAE attack (ie, allergic reaction, viral cold etc.)?” must be “no”.
- Attack must be unique (attack began > 24 hours from the end of the prior attack);
- Any attack that begins within 24 hours from the end of a prior attack will be combined with the prior attack;

- If the entire adjusted attack is untreated, it must have a duration > 24 hours.

Using the above criteria, adjusted attacks will be determined programmatically. For adjusted attacks that span 2 or more subject-reported attacks, attack triggers, locations, symptoms, duration, and other characteristics will be based on the information from each component subject-reported attack. Additionally, the start date/time of the adjusted attack will be the start date/time from the first attack and then end date/time of the adjusted attack will be the end date/time from the last attack being collapsed programmatically.

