6.7.7.3. Baseline Attack Rate

The baseline attack rate will be calculated using data from the SOC period and standardized to number of attacks per month, where 1 month is defined as a 28-day (4 week) period. It is calculated as:

$$\frac{\text{Number of HAE attacks during the SOC period Screening} * 28}{\text{Study Day 1 Date} - \text{Screening Date} + 1}$$

where the number of HAE attacks during SOC period includes any attacks starting after informed consent through the time of first dose. The screening day is the first day of the SOC period. Note that the SOC period starts upon signing the informed consent form. A similar method will be used to calculate other baseline rates (eg, baseline HAE attacks treated with rescue medication).

6.7.7.4. Attack Rate in Parts 1 and 2

The observed attack rate will be computed as the number of attacks per month, where 1 month is defined as a 28-day (4-week) period.

In general, the formula for computing an attack rate is the number of attacks meeting the attack criteria divided by the duration of the reporting period of interest.

$$\text{Attack Rate} \left(\frac{\text{attacks}}{\text{month}} \right) = \frac{\text{Number of Attacks} * 28}{\text{Duration of Treatment Period of Interest}}$$

For subjects who complete the reporting period of interest, duration of reporting period of interest is defined as the last day in the reporting period – first day in reporting period + 1. For subjects who discontinue treatment prematurely in the reporting period of interest, the duration of reporting period of interest is defined as (last day of treatment +1) – first day in reporting period + 1. For example, if a subject receives the last treatment on Day 13 of Month 3 with 2 attacks between Day 1 and Day 14, that subject will be considered to have had a rate of 4 attacks/month ($2 \times 28/14 = 4$) for Month 3. Both the reporting period and the treatment period have been adjusted to include an additional day as the subject prematurely discontinued dosing in Month 3.

Subject-Reported Attack Rate

Subject-reported attack rates will be computed through Week 12 and through Week 48 (eg, 0-12 weeks and 0-48 weeks).

Adjusted Attack Rate

Adjusted attack rates will be computed for the following reporting periods of interest and expressed in units of attacks/month where 1 month = 28 days:

- During SOC
- By month
- Through Week 12 (eg, 1-12 weeks)
- Through Week 48 (eg, 1-48 weeks)

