Adjusted attack rates will be calculated during the SOC period as well as study Parts 1 and 2. For on-study adjusted attack rates by month, months will be defined in blocks of 28 days, beginning on Day 1, after the first dose of berotralstat. If an attack occurs on Day 1, and the time of both the attack and berotralstat administration are recorded, then an attack prior to berotralstat should be counted in the SOC period and an attack after berotralstat administration should be counted in Week 1 (Month 1). Should a subject prematurely discontinue treatment at the end of the monthly reporting period (ie, Day 28), any attacks that occur within 24 hours after last dose will be counted in the calculation of attack rate of the prior month and the additional 24-hour period will be included in the duration of the reporting period. For example, if a subject has 1 attack from Day 1 to 28, discontinues drug on Day 28, and has an attack on Day 29, the Month 1 (Day 1 to Day 28) attack rate will be 0.55 attacks/month ($2 \times 28/29 = 0.55$). Since HAE attack data are only to be collected during SOC, Part 1, and Part 2, an attack that numerically falls beyond Week 48 will be included with data in Week 48 (Month 12) if it occurs on or prior to the Week 48 visit (also see Table 5).

No imputation will be done for missing data.

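### A stand-alone untreated attack with no recorded stop date and time is always dropped from the adjusted attack rate, however long it lasted

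*SAP*

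**What the plan says.** SAP 8.5.7 fills in incomplete attack times. If the stop date and time are both missing: "The stop date will be set to the attack start date, and the stop time will be set to 11:59PM". If the start time is missing: "The start time will be set to 12:00PM".

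SAP 6.7.7.2 defines the adjusted attack through criteria applied in order. Merging comes first: "Any attack that begins within 24 hours from the end of a prior attack will be combined with the prior attack". The duration test comes last: "If the entire adjusted attack is untreated, it must have a duration > 24 hours".

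SAP 6.7.7.5 counts symptom days from the start and resolution dates of adjusted attacks. SAP 6.7.7.6 takes duration from the start and stop times. SAP 6.7.7.1 counts every subject-reported attack with no duration test.

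On the rate itself, SAP 6.7.7.4 multiplies the number of attacks by 28 and divides by the length of the period. It also says: "No imputation will be done for missing data". Protocol 4.1 describes attacks as rapid in onset, "with symptoms subsiding gradually over the following 3 to 5 days".

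**The concern.** Each rule looks harmless alone. The 24-hour test removes brief untreated swellings, and the stop-date rule completes a record. Used together, they turn a missing date into evidence that the attack was short, and the attack is then removed for being short. The true length never enters.

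Missing stop dates are foreseeable. Under Protocol 10.11 diaries are collected at each visit through Week 48 and staff may not write in them. An attack in progress at collection can therefore lack an end unless the caregiver carries it forward.

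At stake are the adjusted attack rate, the attack durations and the symptom days. These fill most of the effectiveness tables in SAP 14.1, including those for the interim analysis supporting the marketing application. For adverse events, SAP 8.5.8 resolves missing severity and missing relationship conservatively. Here the missing item is resolved toward an attack that did not count.

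**Working it through.** **Rate formula.** SAP 6.7.7.4 gives a worked example of 2 attacks in 14 days: 2 × 28/14 = 4 attacks/month, which reproduces. (The second example in that section does not: 2 × 28/29 = 1.93, where the SAP prints 0.55. That is a separate correction.)

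**Longest imputed duration.** The stop is fixed at 23:59 on the start date.
- Earliest possible start, 00:00: 23 h 59 min = 23.98 h.
- Start time also missing, set to 12:00PM: 11 h 59 min.
- Of the 1,440 possible start minutes, none gives more than 24 h.

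An untreated attack that is not merged with another therefore fails the test with certainty.

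**Effect on one child (illustrative counts).**
- 2 attacks in 84 days: 2 × 28/84 = 0.67. With one deleted: 1 × 28/84 = 0.33.
- 6 attacks in 84 days: 6 × 28/84 = 2.00. With two deleted: 4 × 28/84 = 1.33.
- Over 336 days each deletion costs 28/336 = 0.083 attacks per 28 days.

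**Effect on attacks that are kept.** Take a treated stand-alone attack that truly lasted 3 to 5 days (72 to 120 h).
- Its duration is understated by at least 1 − 23.98/72 = 67% to 1 − 23.98/120 = 80%.
- It counts as one symptom day, although 72 h spans at least three calendar days.

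**Net effect on the adjusted rate.** The stop-date rule can also raise the count. For treated attacks, an early imputed stop widens the gap to the next attack, so two reports that would have merged can count as two. A simulation over 336 days (3,000 children per setting) assumed 20% of stop dates missing at random and true durations uniform from 24.5 to 120 h. The percentage change in the adjusted rate was:

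| Untreated share | 1 attack per 28 days | 2 | 4 |
|---|---|---|---|
| 0% | +1.7 | +3.6 | +7.2 |
| 10% | −0.1 | +1.8 | +5.5 |
| 30% | −4.1 | −1.9 | +2.1 |
| 50% | −8.0 | −5.6 | −1.5 |
| 100% | −17.6 | −15.1 | −10.4 |

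All simulation inputs are assumptions. The documents give neither the untreated share nor the frequency of missing stop dates.

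**Secondary point: the denominator.** SAP 6.7.7.4: "For subjects who complete the reporting period of interest, duration of reporting period of interest is defined as the last day in the reporting period", minus the first day, plus one. Nothing is deducted for an unreturned diary. If a diary interval is lost, nothing is recovered and attacks are evenly spread, the rate falls by the lost fraction. That is 84/336 = 25% for one 12-week diary in Weeks 1-48, and 42/84 = 50% for the Week 6-12 diary in Part 1.

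**The case against.** The strongest case on the other side has five parts.

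1. **Direction.** A reader might infer that the missing-data rules push the attack rate down in general. They do not: the table shows either sign. Other parts of SAP 8.5.7 can also keep short attacks. With both times missing and the stop on the next day, the imputed duration is 35 h 59 min, so a brief untreated attack passes. Every child must also have access to acute medication, which may keep the untreated share low. This stands, and it limits the claim to the class of attacks described.
2. **Bias toward the drug.** This too is tempting and not shown. Adjusted rates in the SOC period use the same rules, so the direction of any before-and-after bias depends on which period has more missing stop dates.
3. **Lost diaries treated as attack-free.** The SAP does not say this; it is an inference from the denominator. Protocol 10.11 says "The P/C will fill out the HAE attack diary whenever an attack (or suspected attack) occurs", which suggests that a blank and a missing diary look alike. But SAP 8.5.7 refers to a dated diary question answered yes or no, and the form is not shown. Diary review at visits, the SOC and Part 2 contacts (Protocol 9.2.2 and 9.4.1) and data cleaning (SAP 6.3) may recover attacks. The 25% and 50% figures are therefore worst cases.
4. **An unaffected measure exists.** Subject-reported rates through Weeks 12 and 48 have no duration test. This holds for counts and rates, but not for durations or symptom days, which still use the imputed stop.
5. **Weight.** Pharmacokinetics is primary; effectiveness is secondary and descriptive, with no hypothesis tested. This lowers the consequence but does not make the rule correct.

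The general statement that missing data are not imputed does not rescue the rule. SAP 8.5.7 is the specific instruction, and it does impute.

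**Conclusion.** The point holds for a defined class. A wholly untreated attack that is not merged with another and has neither stop date nor stop time is removed from the adjusted rate with probability 1, whatever its true length. No other section repairs this. It follows from the two rules alone and needs no assumption about the data. Treated stand-alone attacks with no stop date stay in, but with a duration under 24 h and one symptom day.

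The size for the whole trial cannot be stated, because it depends on two quantities that the documents do not give. The conclusion is that the rule is wrong as written, not that the reported adjusted rate will be too low or will favour berotralstat. The calendar-day denominator is a lesser matter of transparency and need not hold up the plan.

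**What to change.** **Main change (SAP 6.7.7.2 and 8.5.7).**
- Do not use an imputed stop date to apply the 24-hour test.
- Keep an untreated attack with a missing stop date as an adjusted attack unless other recorded data show that it lasted 24 h or less.
- Set its duration to missing in the duration summaries, and do the same for treated attacks with no stop date.
- Report one sensitivity analysis excluding the untreated attacks kept under this rule. Retaining them is also an assumption, and the two results bracket it.
- Apply all of this alike to the SOC period, Part 1 and Part 2, and state how many attacks are affected in each.
- Add a rule for a missing stop date with a stop time present, which SAP 8.5.7 does not cover.

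**Cost.** Revised SAP wording, a flag for missing stop dates and one extra table. Adjusted rates, including the SOC baseline, may rise slightly.

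**Optional.** Where diary-return data allow, report the percentage of days covered by a returned diary in each period, with a sensitivity rate on covered days. This needs coverage data that the documents do not show to exist. It could overstate the rate if diaries go missing mainly in attack-free periods, so it should not replace the planned denominator.

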8.5.8. Missing Severity or Relationship of Adverse Events

Should an event have a missing severity code then the event will be considered to be a Grade 3 (severe) event. If an event has a missing relationship, it will be classified as being related to study treatment.

8.6. Values of Clinical Concern

QTcF intervals >500 msec or a change from baseline in QTcF > 60 msec and a simultaneous absolute QTcF > 460 msec are of clinical concern.

9. STUDY POPULATION

Tables describing the study population as noted below will present summaries by cohort unless otherwise specified.

9.1. Disposition of Subjects

Subject disposition will be presented for all subjects. The number and percentage of subjects included in the ITT, completer, safety, and PK populations will be presented by cohort. The number and percentage of subjects who complete each study part as well as the entire study and those who discontinue from the study will be provided. The reasons for early discontinuation will be presented.

A consolidated standards of reporting trials (CONSORT) diagram will be created based on the summary tables for the study report.

These data will also be listed by cohort and subject.

